	PFS according to RECIST 1.1 assessed by Investigator	Population/Treatment: Same as #1 Intercurrent Event Strategy: 
 Death within 2 missing scheduled tumor assessments after last evaluable assessment or start of study intervention will be considered as event (composite strategy) Discontinuation of treatment: ignoring the intercurrent event (treatment policy strategy) Start of subsequent anticancer therapy: ignoring events after the start of a new anticancer therapy (hypothetical strategy) Population-level Summary: Kaplan-Meier estimates including associated statistics	4
	Locoregional control (LRC) according to RECIST 1.1 assessed by Investigator	Population/Treatment: Same as #1 Intercurrent Event Strategy: 
 Death: Assessments before death will be used (treatment policy strategy) Discontinuation of treatment: ignoring the intercurrent event (treatment policy strategy) Start of new anticancer therapy: ignoring events after the start of a new anticancer treatment (hypothetical strategy) Population-level Summary: Same as #4	5
To evaluate time to subsequent cancer treatments in participants treated with xevinapant when added to weekly cisplatin-based CRT in LA SCCHN	Time to subsequent systemic cancer treatments	Population/Treatment: Same as #1 Intercurrent Event Strategy/ Population-level Summary: Same as #5	6

Overall Design:

This is a multicenter, single arm, open label, Phase 1b study.

Brief Summary: The purpose of this study is to evaluate the tolerability and safety of xevinapant when added to weekly cisplatin-based concurrent CRT in the treatment of participants with unresectable locally advanced squamous cell carcinoma of the head and neck, suitable for definitive chemoradiotherapy.

Study details include:

- Study duration: participants to be followed until the last on-study participant reaches his/her 18-month post-first treatment visit (EOS) a decision to end the study has been triggered, or until premature discontinuation from study, whichever occurs first.
- Treatment duration: 18 weeks, consisting of six 3-week cycles.

- Visit frequency: One to 3 visits a week during combination therapy period, once every 3 weeks during xevinapant monotherapy period, and every 3 months during the Follow-up period until EOS.

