Since treatment is limited to 18 weeks no continued availability of xevinapant outside of the study protocol is foreseen.

Number of Participants: A total of approximately 40 participants will be assigned to study intervention. It is anticipated to conduct the study in the US, Europe, and Asia-Pacific.

Study Intervention Groups and Duration:

Participants who meet the eligibility criteria will be enrolled and will receive the following treatment:

[figure not shown]
- 3 cycles of xevinapant (oral solution **CCI** mg/day from Day 1 to 14, per 3-week cycle) + weekly cisplatin (**CC** mg/m² for 7 weeks on Cycle 1 Day 2 (C1D2), C1D9, C1D16, C2D2, C2D9, C2D16, and C3D2) + IMRT (70 Gy in 35 fractions, 2 Gy/fraction, 5 days/week), followed by 3 cycles of monotherapy of xevinapant (**CCI** mg/day from Day 1 to 14, per 3-week cycle).

Data and Safety Monitoring /Other Committee: Yes

A Safety Monitoring Committee (SMC) has been appointed for this study. The SMC consists of Sponsor representatives and the Coordinating Investigator.

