- Xevinapant doses that were omitted on a specific day should **NOT** under any circumstances be administered any other day in addition to the scheduled intake.
- No additional dose should be re-administered after vomiting; the participant must wait for the next scheduled intake.
- Combination treatment period: If IMRT is interrupted, xevinapant should be interrupted. If IMRT is restarted, xevinapant should be resumed at the next originally scheduled intake day of xevinapant, provided other rules of dose interruption are not met (see Section 6.5.3.3). If IMRT is permanently discontinued due to safety issues, then xevinapant administration should be maintained, and the participant can enter the monotherapy period. Otherwise, xevinapant treatment should be discontinued permanently, the EOT visit should be performed, and the participant should stay on study for follow-up as per protocol. IMRT may be interrupted for up to a maximum of 10 treatment days in total.
- Monotherapy treatment period: If a participant requires a xevinapant dose interruption of more than 21 consecutive days due to study intervention-related toxicities, the Investigator should consider discontinuing the treatment. If a participant is discontinued from the monotherapy treatment, the EOT visit should be performed. Hereafter, the participant will continue with the study as per schedule and will enter the FU period.
- Chemotherapy discontinuation will **NOT** result in xevinapant discontinuation.
- Participants who prematurely discontinue from all treatments, i.e. chemotherapy, IMRT, and xevinapant, in the absence of disease progression will undergo the EOT visit and then enter the follow-up period according to schedule.
- Any dose modification and dose interruption including the reason must be recorded on the Dosage Administration Record eCRF.

CCI

CCI

CCI

CCI

CCI

[figure not shown]
CCI

CCI

CCI

CCI

CCI

[figure not shown]

CCI

CCI

CCI

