# 7 Changes to the Planned Analyses in the Clinical Study Protocol

## 7.1 Overview of Planned Analyses after discontinuation of Xevinapant trials

A review of the TrilynX study (MS202359\_0006) data suggests that the experimental arms with Xevinapant demonstrated either lower efficacy compared to the control group or limited potential for added benefit over standard of care.

Consequently, the scope of analyses for this study (MS202359\_0025) has been reduced. The analyses outlined in Section 6 will not be conducted as originally planned. However, following analyses will be performed instead:

- an analysis for the first SMC with 6 patients,

- an analysis using the primary analysis DBL date of 20-SEP-2024 for a synoptic CSR.

The analyses considered relevant for a synoptic CSR are listed below:

- Study Subject Data:
  - Participant disposition
    - Subject Disposition Status
    - Analysis Sets
  - Enrollment details
  - Demographic Characteristics
  - Medical History
  - Other Baseline characteristics
    - Disease History
  - Previous and Concomitant Medications, Procedures, Follow-up Treatments
    - Previous Medication
    - Concomitant Medication
    - Concurrent Procedures
  - Treatment Compliance and Exposure
    - Duration of Therapy
    - Cumulative Dose, Dose Intensity, Relative Dose Intensity
    - Dose Reductions
    - Therapy Delays
- Safety Data:
  - Display of Adverse Events
    - Overview of Treatment Emergent Adverse Events (TEAEs)
    - Overview of TEAEs Leading to Discontinuation / Dose Reduction of Treatment
    - TEAEs by Primary System Organ Class (SOC) and Preferred Term (PT)
    - Study Intervention Related TEAEs by SOC and PT
    - Serious TEAEs by SOC and PT
    - Non-serious TEAEs by SOC and PT at a Frequency Threshold of 5%
    - TEAEs by Worst Grade, SOC and PT
    - Study Intervention Related TEAEs by Worst Grade, SOC and PT
  - Deaths, Other Serious and Significant Adverse Events

- Deaths by Primary Reason
- Listing of Deaths
- Listing of Serious TEAEs
- Clinical Laboratory Evaluations
  - Hematology - Summary Statistics over Time
  - Hematology - Shift in Toxicity Grading from Baseline to Highest Grade
  - Biochemistry - Summary Statistics over Time
  - Biochemistry - Shift in Toxicity Grading from Baseline to Highest Grade
- Other Safety Evaluations
  - Vital Signs Results Summary Statistics Over Time
  - ECG Results - Summary Statistics Over Time
- Subject Data Listings:
  - Discontinued Subjects

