## 13 Study Intervention: Compliance and Exposure

The following analyses will be performed based on SAF.

All dosing calculations and summaries will be based on “Study Drug Administration” CRFs pages.

If the total dose is missing, the protocol defined dose of each study intervention will be used.

No imputation of missing start dates of study interventions will be done.

In case the last date of study intervention is incomplete the date of last study intervention administration will be taken from the End of Treatment page.

For Cycle X, actual cycle start date for each participant is:

- the earliest start date of dosing in the Cycle X Day 1 visit eCRF exposure page, if the participant received any study intervention on that visit (i.e., any study intervention with dose>0 at that visit)
- the first day of assessments in the Cycle X Day 1 visit, if the participant did not receive study intervention on that visit (i.e., all study interventions had dose=0 at that visit). Use start date in the exposure page if available; if start date is not available then use date of collection of vital signs (assuming vital signs are the first assessment of the cycle on Cycle X Day 1 visit).

Actual cycle end date for each participant is:

- for all cycles X except the last cycle, actual cycle end date = actual cycle (X+1) start date – 1 day;
- for the last cycle, actual cycle end date = actual cycle start date + intended cycle duration (in days) – 1 day

Cycle duration (weeks) = (actual cycle end date – actual cycle start date + 1)/7

When summarizing exposure for each study intervention, only cycles with non-zero dose of study intervention of at least one of the study interventions should be included.

A dose is regarded to be administered, if the actual dose received is > 0, or the duration of the infusion is > 0, or the start date or end date is not missing.

**Xevinapant Cumulative dose (mg)** overall is the sum of the actual doses of study intervention received overall. Actual dose per day is collected using mL on eCRF. This dose will be converted to mg as:

$$\text{Actual dose (mg)} = \text{Actual dose (mL)} * 20 \text{ (mg/mL)}$$

**Xevinapant Dose intensity (mg/day)** is defined as the cumulative dose of xevinapant by the cycle duration in days as:

$$\text{dose intensity} = \left( \frac{\text{cumulative dose}}{(\text{planned dosing days per cycle (14 days)}) * \text{exposure duration (cycles)}} \right)$$

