**Cisplatin/carboplatin Cumulative dose (mg/m^2 or AUC)** overall is the sum of the actual doses of study intervention received overall, respectively.

**Cisplatin/carboplatin Dose intensity (mg/m^2/day or AUC/day)** is defined as the cumulative dose of cisplatin/carboplatin by the exposure duration in days as:

$$\text{dose intensity} = \left( \frac{\text{cumulative dose}}{(\text{planned dosing days per week (1 day)}) * \text{exposure duration (weeks)}} \right)$$

**IMRT Cumulative dose (Gy)** overall is the sum of the actual doses of study intervention received overall. If a IMRT dose modification will occur PTV1 new reported value will be used for the calculation.

**IMRT Dose intensity (Gy/day)** is defined as the cumulative dose of IMRT by the exposure duration in days as:

$$\text{dose intensity} = \left( \frac{\text{cumulative dose}}{(\text{planned dosing days per week (5 days)}) * \text{exposure duration (weeks)}} \right)$$

**Relative dose intensity (%)** is defined as the actual dose intensity divided by the planned dose intensity during the study and expressed in percentage:

$$\text{relative dose intensity} = \left( \frac{\text{dose intensity}}{\text{planned dose}} \right) * 100$$

Where the planned dose is:

- Xevinapant: **CCI** mg/day
- Cisplatin: **cci** mg/m^2/day
- Carboplatin: AUC2/day
- IMRT: 70 Gy/day

The summary of study intervention exposure will include the following information:

- Total duration of xevinapant, cisplatin, carboplatin and IMRT (weeks) and by categories of  $\leq$  3 weeks,  $> 3 - 6$  weeks,  $> 6 - 9$  weeks,  $> 9 - 12$  weeks,  $> 12 - 15$  weeks,  $> 15 - 18$  weeks
- Number of IMRT Fractions
- Total number of cycles received of xevinapant, cisplatin, carboplatin and IMRT
- Cumulative dose of xevinapant, cisplatin, carboplatin and IMRT
- Dose intensity of xevinapant, cisplatin, carboplatin and IMRT
- Relative dose intensity (%) of xevinapant, cisplatin, carboplatin and IMRT
- Dose reduction of xevinapant, cisplatin, carboplatin and IMRT per time period (overall and by reason)
- Missed doses of xevinapant, cisplatin, carboplatin and IMRT per time period
- Discontinuation of xevinapant, cisplatin, carboplatin and IMRT per time period (overall and by reason)
- A listing will be provided for all administrations of participants for the primary analysis only.

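### On its visible text, SAP 13 drops a fully withheld xevinapant monotherapy cycle from the dose-intensity denominator, so relative dose intensity can read 100% where 83.3% of the planned dose was given

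*SAP*

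**What the plan says.** SAP 13 defines xevinapant dose intensity as cumulative dose divided by the product of "planned dosing days per cycle (14 days") and "exposure duration (cycles"). RDI "is defined as the actual dose intensity divided by the planned dose intensity during the study and expressed in percentage". In the same section, the rule for which cycles enter the exposure summaries is that "only cycles with non-zero dose of study intervention of at least one of the study interventions should be included".

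Protocol 1.1 gives "Treatment duration: 18 weeks, consisting of six 3-week cycles". The first three cycles combine xevinapant with weekly cisplatin and IMRT, "followed by 3 cycles of monotherapy of xevinapant".

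Protocol 6.5.1.2 does not allow omitted xevinapant doses to be made up on another day. In the monotherapy period it asks the investigator to consider stopping treatment "If a participant requires a xevinapant dose interruption of more than 21 consecutive days due to study intervention-related toxicities". Protocol 1.3 ties visit days to C1D1, so a withheld cycle is lost rather than shifted.

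SAP 7.1, which sets the reduced scope for the synoptic CSR, keeps "Cumulative Dose, Dose Intensity, Relative Dose Intensity".

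**The concern.** The inclusion rule is written across interventions, but xevinapant dose intensity belongs to one intervention. In Cycles 1 to 3 the difference rarely matters: if xevinapant is withheld for a whole cycle while cisplatin or IMRT continues, the cycle stays in and the lost doses lower RDI. In Cycles 4 to 6 nothing else is given. A cycle with no xevinapant then fails the rule and disappears from the denominator, having added nothing to the numerator.

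The same loss of 14 dosing days is therefore penalised in one phase and ignored in the other. Within the monotherapy phase, a participant who takes no doses in a cycle scores better than one who takes a few. RDI is one of the treatment-delivery summaries kept for the synoptic CSR, and it would be most favourable for the cycles with the least delivery. The rule works this way whatever the reason for withholding, toxicity or otherwise.

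**Working it through.** The documents state no RDI figure, so there is none to reproduce. The check applies the SAP 13 formula directly.

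**Inputs**
- Six planned cycles (Protocol 1.1), with 14 planned xevinapant days per cycle (SAP 13): 6 × 14 = 84 planned daily doses.
- Cycles 4 to 6 contain xevinapant only (Protocol 1.1).
- The planned daily dose is redacted. It cancels in RDI, so it is set to 1.
- All doses not named as omitted are assumed taken in full at the planned level.

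**Formula**

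RDI = 100 × [cumulative dose / (14 × number of included cycles)] / planned daily dose

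**Results**

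| Scenario | Dosing days taken | Cycles included under SAP 13 | RDI under SAP 13 | RDI with all six planned cycles |
|---|---|---|---|---|
| No omission | 84 | 6 | 84/84 = 100% | 84/84 = 100% |
| Cycle 4, 5 or 6 withheld in full | 70 | 5 | 70/70 = 100% | 70/84 = 83.3% |
| Xevinapant withheld throughout Cycle 2, cisplatin or IMRT given | 70 | 6 | 70/84 = 83.3% | 70/84 = 83.3% |
| 7 of 14 doses taken in Cycle 5 | 77 | 6 | 77/84 = 91.7% | 77/84 = 91.7% |
| 1 of 14 doses taken in Cycle 5 | 71 | 6 | 71/84 = 84.5% | 71/84 = 84.5% |

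Rows two and three are the same loss, 14 dosing days, with two different answers. Rows five and two show that the measure is not monotone: RDI goes from 84.5% with one dose to 100% with none.

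If other doses were reduced or missed, the numerator changes but the ratio of the two denominators does not. With one cycle withheld, RDI is too high by (14 × 6)/(14 × 5) = 6/5.

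**Can a whole cycle be withheld and dosing resume?** Protocol Table 3 puts C4D1 on Day 64 and C5D1 on Day 85. Withholding Cycle 4 leaves Days 64 to 84 without drug: 85 − 64 = 21 days, which is not more than 21. If the planned rest week of Cycle 3 were also counted (Days 57 to 63), the gap would be 28 days. Even then the protocol asks only that discontinuation be considered.

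**Does a zero-dose cycle exist as a record?** Yes. SAP 13 sets a cycle start date from the Day 1 visit assessments when no intervention was given at that visit. An undosed Cycle 5 therefore has its own start and end dates and is not absorbed into Cycle 4. The inclusion rule is what removes it.

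**The case against.** The strongest objection is that the deciding definition may be out of sight. SAP 13 divides by exposure duration in cycles without defining it there, and SAP 9.9 (Exposure time) is redacted. If 9.9 counts from first to last dose, a withheld Cycle 4 or 5 reads 83.3%; a withheld Cycle 6 would still read 100%. SAP 13 also treats a dose as administered when a start or end date is present, so a dated record with zero dose might be kept. Both points stand as conditions on the 100% figure. Neither removes the problem: each would conflict with the visible non-zero-dose rule, and the passages would need reconciling. The monotherapy dose-modification table (Protocol Table 8) is also redacted and may limit how often a full cycle is withheld.

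Four stronger readings are tempting, and the documents do not support them.

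- *That the loss is concealed altogether.* SAP 7.1 keeps cumulative dose, therapy delays and a participant-level listing of compliance and exposure. Cumulative dose would show 70 of 84 planned daily doses. SAP 13 also has a missed-dose summary, although the 7.1 list does not name it.
- *That RDI is the study's leading tolerability measure.* The primary endpoint is DLT-like events in the first five weeks, and SAP 7.1 keeps several adverse-event and laboratory summaries. RDI is one exposure line among them.
- *That the rule also dilutes cisplatin and IMRT intensity by bringing in Cycles 4 to 6.* Those formulas use exposure duration in weeks, and no visible text sums weeks over xevinapant-only cycles.
- *That two consecutive withheld cycles are an ordinary case.* That is 2 × 21 = 42 days, beyond the 21-day point at which discontinuation is to be considered. The finding rests on one withheld cycle.

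**Conclusion.** The point holds on the visible text of SAP 13. For one fully withheld monotherapy cycle, xevinapant RDI reads 100% instead of 83.3%, an overstatement of 16.7 percentage points. It is an inflation by 6/5 when other doses are incomplete. The 100% figure assumes that all other doses were taken in full, that SAP 9.9 does not define duration as a calendar span, and that a dated zero-dose record is not counted as administered.

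The consequence is limited to a descriptive exposure summary. No hypothesis is tested (Protocol 9.1). The 60% cumulative-dose criterion for the DLT analysis set concerns the first five weeks and is unaffected. A correction is still worthwhile: the output is retained, and a delivery measure that improves when the last dose of a cycle is dropped can mislead.

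**What to change.** Replace the inclusion sentence in SAP 13 with:

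> For each study intervention, all cycles in which that intervention was planned are included, from its first dose until its completion or recorded permanent discontinuation. A planned cycle in that span with no dose, including a withheld final cycle, counts as zero dose and stays in the denominator. Cycles in which the intervention is not planned are not included.

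Align SAP 9.9 with this, and likewise the SAP 13 sentence on when a dose counts as administered, so that a zero-dose record is treated in one way throughout.

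The endpoint of the span matters. A span ending at the last dosed cycle would restore 83.3% for a withheld Cycle 4 or 5 but leave 100% for a withheld Cycle 6. Ending it at completion or recorded permanent discontinuation covers all three. RDI still describes delivery while on treatment: a participant who permanently stops after three full cycles keeps 42/42 = 100%, and the early stop appears in duration of therapy.

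The cost is one sentence and a small programming change. SAP version 2.0 (14 March 2025) uses a database lock of 20 September 2024, so this would be a change after lock and should be reported as such in the CSR. Some RDI values will become less favourable.

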### **15.3 Deaths, Other Serious Adverse Events, and Other Significant Adverse Events**

#### **15.3.1 Deaths**

All deaths, deaths within 30 days after last dose of study intervention, death within 60 days after first dose as well as reason for death, will be tabulated based on information from the "Death" page in eCRF:

- Number of Deaths
- Number of Deaths within 30 days after last dose of each study intervention
- Number of Deaths within 30 days after last dose of any study intervention
- Number of Deaths within 60 days after first dose of any study intervention
- Primary Reason of Death:
  - Disease progression
  - AE related to study intervention
  - AE not related to study intervention
  - Other
  - Unknown

In addition, date and cause of death will be provided in individual participant data listing together.

This listing will include:

- AEs with fatal outcome (list preferred terms of AEs with outcome=fatal)
- Flag for death within 30 days of last study intervention
- Flag for death within 60 days of first study intervention

Where AE related/not related to study intervention in Primary Reason of Death is defined as patients with:

- Related = 'What is the primary cause of death?' in "Death" page in eCRF is 'Adverse Event' and at least 1 fatal AE related to any study intervention
- Not related = 'What is the primary cause of death?' in "Death" page in eCRF is 'Adverse Event' and no fatal AE related to any study intervention

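### SAP Section 13 counts a recorded dose of 0 as administered if the record carries a date, so exposure output can depend on how withheld doses are entered

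*SAP*

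**What the plan says.** SAP Section 13 defines an administered dose in one sentence. A positive actual dose qualifies, "or the duration of the infusion is > 0, or the start date or end date is not missing". Any one of the three is enough, and nothing ties the second and third to an empty dose field.

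Four other rules in Section 13 bear on it:

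- **Cycle start date.** A fallback date applies "if the participant did not receive study intervention on that visit (i.e., all study interventions had dose=0 at that visit"). For that visit the analyst is told: "Use start date in the exposure page if available; if start date is not available then use date of collection of vital signs".
- **Missing dose.** "If the total dose is missing, the protocol defined dose of each study intervention will be used". This covers an empty dose field, not a recorded 0.
- **Cycles included.** Exposure summaries keep a cycle if at least one study intervention had a non-zero dose in it.
- **Cumulative dose.** It is the sum of actual doses.

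Section 13 also plans a summary of "Missed doses of xevinapant, cisplatin, carboplatin and IMRT per time period" and a listing of all administrations. SAP 15.3.1 plans a "Number of Deaths within 30 days after last dose of each study intervention", and a death listing with a flag for death within 30 days of the last study intervention.

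SAP 7.1 reduces the scope to a synoptic report. It keeps duration of therapy, cumulative dose, dose intensity, RDI, dose reductions, therapy delays, deaths by primary reason, the listing of deaths and a listing of compliance and exposure.

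**The concern.** Section 13 classifies the same kind of record in two ways. A dose = 0 record with a start date means not received when the cycle start is set, and administered when the dose is classified. A programmer who follows the text literally will count a withheld dose as given whenever the site filled in a date. Two participants with identical treatment could then get different exposure results because of data entry alone.

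Tolerability is the trial's primary objective, and exposure output shows how much of the regimen was deliverable. Whether a withheld dose counts as given should not be left to a date field.

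**Working it through.** The SAP states no figure on this point, so there is none to reproduce. The check applies the rule to the planned cisplatin schedule.

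**Inputs**

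- Seven weekly infusions on study Days 2, 9, 16, 23, 30, 37 and 44 (protocol Section 1.3, Table 2 and the notes to Figure 3).
- SAP rule: administered if dose > 0, or duration > 0, or a date is present.
- Comparison rule: administered only if dose > 0. All dose fields are filled in this example.
- Cisplatin dose intensity = cumulative dose ÷ (1 planned dosing day per week × exposure weeks); RDI = dose intensity ÷ planned dose × 100 (SAP Section 13). Each full infusion is set to 1 dose unit.
- Assumption: exposure weeks = (last administered day − first administered day + 7) ÷ 7. SAP Section 9.9 on exposure time is redacted, so the actual formula cannot be seen.
- Assumption: withheld cisplatin is entered as dose = 0 with a date.

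**Last two infusions withheld (Days 37 and 44)**

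- SAP rule: last dose Day 44; weeks = (44 − 2 + 7) ÷ 7 = 7; cumulative dose 5; RDI = 5 ÷ 7 = 71.4%.
- Positive-dose rule: last dose Day 30; weeks = (30 − 2 + 7) ÷ 7 = 5; cumulative dose 5; RDI = 5 ÷ 5 = 100%.
- The last-dose date differs by 44 − 30 = 14 days.

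| Withheld, entered as dated 0 | Administered: SAP / positive dose | Cumulative dose, both rules | Weeks: SAP / positive dose | RDI: SAP / positive dose |
|---|---|---|---|---|
| Infusion 7 | 7 / 6 | 6 | 7 / 6 | 85.7% / 100% |
| Infusions 6, 7 | 7 / 5 | 5 | 7 / 5 | 71.4% / 100% |
| Infusions 5, 6, 7 | 7 / 4 | 4 | 7 / 4 | 57.1% / 100% |
| Infusions 3, 4 | 7 / 5 | 5 | 7 / 7 | 71.4% / 71.4% |

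The table shows three things:

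- The count of administrations is wrong in every row under the SAP rule.
- Duration and RDI change only when the zeros come at the end.
- Cumulative dose never changes, because a zero adds zero.

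If the withheld records carry no date (and no duration), the SAP rule gives the same results as the positive-dose rule in every row. If missed doses are taken as planned minus administered, the SAP rule reports 0 missed in every row; the true numbers are 1, 2, 3 and 2. The SAP does not define missed doses, so that subtraction is also an assumption.

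**Does the included-cycles rule catch this?** Only when every intervention is zero for the whole cycle. Protocol Section 6.5.1.2 says that stopping chemotherapy does not stop xevinapant, so a cycle with cisplatin withheld and xevinapant given stays in.

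**The 30-day flag in the death listing.** The flag refers to the last study intervention overall. Cycle 6 starts on Day 106 (protocol Table 3), so planned xevinapant runs to Day 106 + 13 = 119. Cisplatin zeros at Days 37 and 44 leave the flag unchanged in a participant who continues xevinapant. The flag moves only if a dated zero is the last record of any intervention. For example, take a participant whose last real xevinapant dose is Cycle 5 Day 14 (Day 85 + 13 = 98) and whose Cycle 6 Day 1 is entered as a dated 0. The last-dose date would be Day 106 instead of Day 98, 8 days later, if it follows the rule.

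**The case against.** The case on the other side has several sound parts.

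- **Intent.** The date alternative probably exists for records with a missing dose. That is the natural purpose, but no visible text says so, and the missing-dose rule is a separate sentence that does not reach a recorded 0.
- **Evidence for dated zeros.** The only text that expects them concerns Day 1 visits. Cisplatin is given on Days 2, 9 and 16 of a cycle, and the eCRF is not in the documents. The cisplatin example therefore rests on an assumption about data entry. Protocol Sections 6.5.1.2 and 6.5.2.2 do require interruptions and their reasons on the dosing pages, which makes such records plausible but does not show their form.
- **Degree of contradiction.** The cycle-start rule assigns a calendar date, and the included-cycles rule works across all interventions. Neither defines an administered dose. The direct conflict is with the phrase that equates dose = 0 with not receiving study intervention. That conflict stands.
- **Derived dates.** No visible text says that first and last dose dates or exposure time use the administered-dose rule. SAP Section 9 is redacted and might settle this.
- **Missed doses.** They could be taken directly from the recorded deviations and interruptions, without this rule.

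A reader might infer that the synoptic report will misstate missed doses and per-intervention deaths within 30 days. The documents do not support this: both are planned in SAP Sections 13 and 15.3.1, but SAP 7.1 lists neither. A reader might also infer that cumulative dose, or membership of the DLT analysis set, is inflated. Cumulative dose sums actual doses, and the 60% dose criterion for that set is unaffected if it is computed from actual doses.

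**Conclusion.** The administered-dose rule is wrong as written. It counts any dated zero as a dose given and conflicts with the meaning of dose = 0 in the same section. It does not follow that withheld doses in general are counted as given: a withheld dose with neither a date nor a duration on its record is classified correctly.

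The consequence that needs no assumption about derived dates is in the listing of administrations. Effects on duration of therapy, dose intensity and RDI, all kept in SAP 7.1, require that dose dates and exposure time follow this rule. The 30-day flag in the death listing also requires that the zero be the last record overall. Under those assumptions, with two trailing cisplatin infusions withheld and dated, duration is 7 weeks against 5 and RDI is 71.4% against 100%.

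The error has no single direction: the literal rule raises the number of administrations and the duration but lowers RDI. How often dated zeros occur cannot be told from the documents. The affected output is descriptive, so this is a modest defect, but it is clear and cheap to remove.

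**What to change.** Replace the sentence in SAP Section 13 with a rule in this order:

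1. A dose is administered if the actual dose is greater than 0.
2. Only if the actual dose is missing, it is administered when the infusion duration is greater than 0 or a start or end date is present.
3. A recorded dose of 0 is never an administration.

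State that this definition governs first and last dose dates, exposure duration and any count of missed doses, and align SAP Section 9 with it.

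The cost is one SAP sentence and one change to a derivation, with no new data. A count of dose = 0 records that carry a date or duration in the locked database would show at once whether any retained table or listing changes.
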